9.1.4 Severity

Definitions for classification of severity appear below in Table 9.1. The Investigator will review these definitions with the subject for use when completing the subject diary. For events reported on the AE eCRF, e.g., ISRs that persist beyond the diary period and other AEs, the Investigator will determine the severity classification based on these definitions, his/her experience in the use of dermal fillers, and/or the subject's description of the event.

Note: A "severe" AE is not the same as an "SAE", which is defined above. Seriousness of AEs is defined in *Section 9.1.2: Serious Adverse Events (SAE)*.

Clinical Study Protocol: CMO-MA-FAS-0513

Table 9.1 Classification of Adverse Events by Severity

Mild:	Symptoms are barely noticeable or do not make the subject uncomfortable. The AE/ISR does not interfere with performance or functioning. Prescription drugs are not ordinarily needed for relief of symptoms.
Moderate:	Symptom are of sufficient severity to make the subject uncomfortable. Performance of daily activities is influenced. Treatment of symptom(s) with prescription drugs/therapies may be needed.
Severe:	Symptoms are of such sufficient severity to cause the subject severe discomfort. Performance of daily activities is compromised. Treatment of symptom(s) with prescription drugs/therapies may be needed.
Not applicable:	In some cases, an AE/ISR may be an “all or nothing” finding that cannot be graded.

9.1.5 Relationship to Study Medication or Study Device

A determination will be made, by the Investigator, of the relationship (if any) between an AE and the study drug, anesthesia employed, the study device, or the injection procedure, as applicable. A causal relationship is present if a determination is made that there is a reasonable possibility that the AE may have been caused by the drug, device, or study procedure.

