7.1.7 Biopsy

Subjects who consent to participate in the optional Biopsy Sub-study will have a biopsy sample collected at least 4 weeks prior to the first BELKYRA® treatment at Visit B1. Biopsy sample collection may occur on the same day as Screening (Visit 1) if all eligibility criteria are confirmed prior to performing the biopsy. A second biopsy sample will be collected 8 weeks following the last BELKYRA® treatment at Visit B2. When the second biopsy lesion is healed (at least 4 weeks), VOLUMA™ treatment may occur (see Figure 3.1).

Biopsy samples, approximately 2 mm, will be excised from the submental area approximately 1.5 cm left and right of midline (baseline and post-treatment, respectively). Biopsy samples will be transferred to 10% neutral buffered formalin and shipped to a central laboratory for histopathology.

Additional details on biopsy logistics (e.g. sample collection, fixative, shipping) will be available in the Biopsy Manual.

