2.1 Study Design

This Phase IV trial is a prospective, open-label, multi-center, interventional, drug and medical device, post-marketing study. Each subject will act as his/her own control. Subjects will attend a minimum of 6 and maximum of 18 visits.

Approximately 50 male and female subjects will be treated. Approximately 10 of them are expected to participate in the Biopsy Sub-study.

All subjects will sign an informed consent form (ICF) at the Screening Visit (Visit 1). Eligible subjects will undergo treatment with BELKYRA injected into subcutaneous pre-platysma fat tissue in the submental area (Visit 2.1/Day 0). Seven days after the initial BELKYRA treatment (Visit 3.1), the subject will return to the clinic for a safety evaluation. Eight weeks after BELKYRA treatment, the submental profile will be evaluated by the investigator and the subject. If further BELKYRA intervention is required to achieve the desired result, subjects may receive up to 5 optional BELKYRA treatments (Visits 2.2 to 2.6), for a maximum of 6 treatments including the initial required treatment. Subjects who receive optional BELKYRA treatments will be contacted by telephone 7 days after treatment for safety evaluation (Visits 3.2 to 3.6). The submental profile will be assessed as described 8 weeks after each BELKYRA treatment, and a decision made if further BELKYRA treatments are desired.

When the investigator and the subject agree that no further BELKYRA intervention is required to achieve the desired result, the subject may receive VOLUMA treatment (Visit 4). Fourteen days after VOLUMA treatment, subjects will return to the clinic (Visit 5) and the investigator will assess whether a VOLUMA touch up treatment is to be performed. All subjects will attend a final exit visit (Visit 6) which is 4 weeks after the last VOLUMA treatment (Visit 4 if no touch-up done or Visit 5, if touch-up was performed).

Subjects will have the option of participating in a Biopsy Sub-study. Participation in the sub-study is voluntary and will not affect the subject's eligibility to participate in the main study. Biopsy samples will be collected from the submental region at 2 time points: Visit B1 will occur at least 4 weeks before the first BELKYRA treatment (at Visit 2.1); Visit B2 will occur 8 weeks after the last BELKYRA treatment and at least 4 weeks prior to VOLUMA treatment (at Visit 4). Histological changes from baseline to after final BELKYRA treatment(s) will be evaluated.

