7.2 Adverse Events

Adverse events (AE) will be coded using MedDRA v20.1 or later to give a PT and a SOC term for each event.

An AE is defined as any untoward medical occurrence in a clinical investigational patient administered a pharmaceutical (investigational) product or any undesirable physical, psychological or behavioral effect experienced by a subject during his/her participation in a study, in conjunction with the use of the device and which does not necessarily have to have a causal relationship with this treatment.

All AEs will be included in by-subject AE listings. A separate listing will be created with all the distinct levels of SOC and PT, and the verbatim investigator description reported in the study. Sorting will be by earliest observed SOC, PT within SOC and then verbatim description.

A treatment-emergent adverse event (TEAE) is a post-baseline AE where (i) there is no pre-treatment AE of the same MedDRA primary SOC and PT; or (ii) the maximum severity during the post-baseline period is greater than the maximal severity of any pre-treatment AE of the same MedDRA primary SOC and PT during the enrollment visit. Note that the post-baseline period of the study starts upon the initiation of the BELKYRA treatment at Visit 2.1/Day 0.

Partial or missing AE start dates will be handled as per Section 3.3.3.1.

An overall summary of frequency count and the binomial incidence rate with associated 95% CIs will be presented to describe the incidents of TEAEs. Note that 95% CIs of the binomial incidence rate will be presented for the overall summary analyses of TEAEs, but not for the by-visit analyses. Percentages and corresponding 95% CIs will be displayed to 1 decimal place.

Each type of AE will be tabulated by SOC and PT within SOC. The SOC and PT within SOC will be sorted by descending frequency. Number of subjects with percentage and number of events will be presented based on SOC and PT.

The incidence of all TEAEs by SOC and PT will be presented for the following categories:

- Any TEAE
- Any TEAE related to BELKYRA
- Any TEAE related to VOLUMA
- Any TEAE related to anesthesia
- Any TEAE related to study procedure
- Any TEAE related to BELKYRA/VOLUMA and leading to discontinuation of treatment with BELKYRA/VOLUMA
- Any TEAE by maximum severity

The following listing will be provided:

- Listing of all TEAE

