7.3 Serious Adverse Events

A serious adverse event (SAE) is any AE occurring at any dose that results in any of the following outcomes: death, a life-threatening AE, inpatient hospitalization or prolongation of existing hospitalization, a persistent or significant disability/incapacity, or a congenital anomaly/birth defect. While an unanticipated adverse device effect (UADE) is any device-related SAE that meets one or more of the criteria listed in the Sec. 9.1.3 of the Protocol in page 49.

An overall summary of frequency count and the binomial incidence rate with associated 95% CIs will be presented to describe the incidents of treatment emergent SAEs. Note that 95% CIs presented are for the overall summary analyses of SAE, but not for the by-visit analyses. Percentages and corresponding 95% CIs will be displayed to 1 decimal place.

The incidence of all treatment-emergent SAEs by SOC and PT within SOC will be presented for the following categories:

- Any SAE
- Any SAE related to BELKYRA
- Any SAE related to VOLUMA
- Any SAE related to anesthesia
- Any SAE related to study procedure

- Any SAE related to BELKYRA/VOLUMA treatment and leading to discontinuation of treatment
- Any SAE by maximum severity

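### Protocol 9.1.5 wavers between injection procedure and study procedure and never names the biopsy, while the SAP's single procedure row would pool second-biopsy reactions with injection events over the whole safety population

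*Protocol*

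**What the plan says.** **Causality.** The first sentence of Protocol 9.1.5 requires a judgment on the "relationship (if any) between an AE and the study drug, anesthesia employed, the study device, or the injection procedure, as applicable". The second says a causal relationship is present if "there is a reasonable possibility that the AE may have been caused by the drug, device, or study procedure". The first is limited to injections and the second is not. The biopsy is named in neither.

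**Tabulation.** SAP 7.2 has one category, "Any TEAE related to study procedure", and SAP 7.3 has its counterpart, "Any SAE related to study procedure". Neither separates injections from biopsies. The opening of SAP section 7 divides subjects with an event by the number of patients in the safety population. SAP 3.1 includes in that population subjects who were biopsied but never treated.

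**Biopsy.** About 10 of about 50 subjects are expected in the sub-study (SAP section 1). Under Protocol 7.1.7, samples of about 2 mm "will be excised from the submental area approximately 1.5 cm left and right of midline", the region that BELKYRA treats.

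**Timing.** SAP 2.1 states that "Visit B2 will occur 8 weeks after the last BELKYRA treatment and at least 4 weeks prior to VOLUMA treatment". SAP 7.2 states that "the post-baseline period of the study starts upon the initiation of the BELKYRA treatment at Visit 2.1/Day 0".

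**The concern.** The biopsy is an optional research procedure that affects about a fifth of the subjects and would not be part of ordinary use of the two products. Its local reactions arise in the area treated with BELKYRA.

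The procedure row ought to tell a reader how often injecting these products causes trouble. As planned, it may also carry reactions to an excision that most subjects did not have. The same row cannot give the rate of biopsy reactions among those biopsied, because the denominator is everyone in the safety population.

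The two sentences of 9.1.5 add a second difficulty. An investigator who follows the first may leave a biopsy reaction unattributed, or assign it to the drug or the anesthesia. One who follows the second may call it procedure-related. Identical events could then land in different rows.

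**Working it through.** The plan states no figure for biopsy reactions, so there is nothing to reproduce. The check has two parts.

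**1. Where a B2 reaction goes**

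- The treatment-emergent window opens at the first BELKYRA injection (SAP 7.2).
- B2 is 8 weeks after the last BELKYRA treatment (SAP 2.1), so a reaction to it starts inside the window.
- Exception: if the subject already had a pre-treatment event of the same system organ class and preferred term, for example after the first biopsy (B1), the B2 reaction counts only if it is more severe (SAP 7.2).
- If judged related to study procedure, the event enters the single procedure row with the injection events. No rule in the SAP separates them. Pooling is therefore an inference from the one undivided row; no sentence states it.

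**2. Possible size**

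Assumptions, not taken from the documents:
- exactly 10 of 50 safety subjects are biopsied, and all reach B2;
- every B2 reaction is treatment-emergent and attributed to study procedure;
- biopsy and injection events are independent.

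Let r be the injection-procedure rate and q the proportion of biopsied subjects with a reaction.

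Pooled rate = [40r + 10(1 − (1 − r)(1 − q))] / 50 = r + 0.2·q·(1 − r)

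| r | q = 10% | q = 50% | q = 90% |
|---|---|---|---|
| 10% | 11.8% | 19.0% | 26.2% |
| 30% | 31.4% | 37.0% | 42.6% |

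For example, with r = 0.10 and q = 0.50: 0.10 + 0.2 × 0.50 × 0.90 = 0.190. The largest possible addition is 10/50 = 20 points (r = 0, q = 1). The smallest is 0.

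**Dilution.** The same biopsy events give very different rates on the two denominators (Clopper-Pearson 95% intervals):

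| Subjects with a biopsy reaction | Of 50 in the safety set | Of 10 biopsied |
|---|---|---|
| 1 | 2.0% (0.1 to 10.6) | 10% (0.3 to 44.5) |
| 3 | 6.0% (1.3 to 16.5) | 30% (6.7 to 65.2) |
| 5 | 10.0% (3.3 to 21.8) | 50% (18.7 to 81.3) |
| 10 | 20.0% (10.0 to 33.7) | 100% (69.2 to 100) |

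**The case against.** The strongest reply is that this is a wording mismatch with little consequence.

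- **Attribution is open.** A reader might infer from the first sentence of 9.1.5 that the biopsy cannot be recorded as a cause. The documents do not support that. The second sentence uses study procedure, the opening of Protocol section 9 refers to events related to treatments or procedures, and the biopsy is described under the heading Study Procedures (7.1). This stands: the defect is inconsistency, not exclusion.
- **Treatment-emergent status does not depend on causality.** It is tempting to say that B2 reactions become treatment-emergent because 9.1.5 omits the biopsy. They do not. Their status follows from onset after Day 0 and the rule on earlier events. Adding a biopsy option would change no event's status.
- **Any TEAE is all-cause by definition.** Biopsy events raise it (an assumed 50% becomes 51.0%, 55.0% or 59.0% for q = 10%, 50% or 90%), but counting them there is correct.
- **Events can be separated by hand.** The SAP has separate rows for BELKYRA and VOLUMA and lists all events by subject. B2 lies weeks away from both injections, and Protocol 9.1.1.2 records onset and location for device events. This shows that a split is feasible, but a listing does not give the rates that a table should.
- **The effect may be small.** The sample is about 2 mm. At q = 10% the row moves by less than 2 points. This stands, and the low end belongs in the range.
- **Unseen material may settle part of it.** The causality field of the case report form and the Biopsy Manual are not among the documents, and the text of the biopsy visits is redacted. A biopsy option may exist on the form. Even then, the SAP as written has no row in which to report it.

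**Conclusion.** The point holds as a reporting weakness. The two causality sentences disagree, neither names the biopsy, and the SAP's single procedure row over the whole safety population would mix and dilute B2 reactions attributed to study procedure.

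The size is unknown because no biopsy reaction rate is given. With 10 of 50 biopsied, the addition to that row lies between 0 and about 20 percentage points. The upper end requires that nearly every biopsied subject reacts, that few of them also have an injection-procedure event, that all these reactions are attributed to study procedure, and that none is removed by the rule on earlier events of the same term.

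A reader might go further and infer that the BELKYRA and VOLUMA rows are contaminated. That would need misattribution by investigators, which the mismatch makes possible but the documents do not show. The study is single-arm and its safety reporting descriptive, so no comparison is biased. The primary efficacy analysis is untouched. This is a cheap improvement to the safety tables, and nothing more.

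**What to change.** 1. In Protocol 9.1.5, make the two sentences use the same terms, and list biopsy procedure as a cause separate from injection procedure.
2. In SAP 7.2 and 7.3, replace the single procedure row with two: injection procedure, with treated subjects as denominator, and biopsy procedure, with biopsied subjects as denominator.
3. If the adverse event form is already fixed, derive the split from onset date and recorded location, and state the derivation rule in the SAP before database lock.
4. Keep Any TEAE as all-cause. A supplementary version without events attributed only to the biopsy is optional.

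The cost is one more causality option, or one derivation rule, and a few table rows. No visits, procedures or staff are added. The biopsy row will rest on about 10 subjects and have wide intervals, as the second table in the working shows.

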9.2 PROCEDURE FOR REPORTING ADVERSE EVENTS

All AEs must be recorded in source documents and on the appropriate eCRF. All AEs that are drug-related and unexpected (not listed as treatment-related in the current Package Insert or Directions for Use) must be reported to the governing IRB as required by the IRB, local regulations, and the governing health authorities. Any adverse event that is marked “ongoing” at the Exit Visit must be followed-up as appropriate.

9.3 PROCEDURES FOR REPORTING AN SAE

Any SAE occurring during the study period (beginning with informed consent) and through 30 days after study exit must be immediately reported on 2 SAE forms. Both drug and device SAE fax forms must be recorded and faxed to the appropriate numbers on the front page of the protocol. All subjects with an SAE must be followed up and the outcomes reported. The Principal Investigator must supply the Sponsor and the IRB with any additional requested information (e.g., hospital discharge summary, autopsy reports and terminal medical reports) if required. The Sponsor shall evaluate all SAEs for both drug and device. Device SAEs will be documented in writing as to whether they meet the definition of an UADE. These shall be reported to all participating Investigators, the regulatory authorities, and the IRB.

In the event of a serious adverse event, the Investigator must:

1. Notify Allergan immediately (within 24 hours) using the SAE reporting forms (for information see page 1 of the protocol). Emergency phone numbers and relevant Allergan personnel contacts are also on the front page of protocol.

Clinical Study Protocol: CMO-MA-FAS-0513

2. Obtain and maintain in his/her files all pertinent medical records, information, and medical judgments from colleagues who assisted in the treatment and follow-up of the subject.
3. Provide Allergan with a complete, written case history (SAE report form) including copies of supporting reports (e.g., progress notes, laboratory reports) and a statement from the Investigator as to whether the event was or was not related to the use of the investigational drug or device.
4. Promptly inform the governing IRB/IEC of the SAE, if it is device-related, as required by the IEC/IRB, local regulations, and the governing health authorities.

9.4 PROCEDURES FOR REPORTING PREGNANCY

If a female of childbearing potential becomes pregnant during the study, the Investigator will notify the Sponsor immediately by completing the Pregnancy Surveillance Form after the pregnancy is confirmed. The subject will be withdrawn from the study per *Section 8.2.1: Withdrawal Criteria*. The Investigator shall (1) notify the subject's physician that the subject was being treated with BELKYRA® or BELKYRA® plus VOLUMA™, as appropriate, and (2) follow the progress of the pregnancy. The Investigator must document the outcome of the pregnancy and provide a copy of the documentation to Allergan.

Pregnancy by itself will not be considered an AE or SAE. Hospitalization for a normal delivery does not constitute an SAE. However, the occurrence of an adverse pregnancy outcome for the mother or child may constitute an AE or SAE, and these should be reported as described in *Section 9.2: Procedure for Reporting Adverse Events*. Allergan considers any abortion (spontaneous or not spontaneous) as an SAE and should be reported as described in *Section 9.3: Procedures for Reporting an SAE*.

10 STATISTICAL METHODS

10.1 GENERAL STATISTICAL CONSIDERATIONS

General statistical analysis methods are provided below; full details will be provided in a separate Statistical Analysis Plan (SAP), which will be finalized prior to database lock.

Data will be summarized using descriptive statistics (number of observations (n), mean, standard deviation, median, minimum, and maximum for continuous variables; and n and percent for categorical variables). Confidence intervals (95%) will be provided for the efficacy endpoints.

Three critical time points, baseline (Visit 2.1/Day 0), Visit 4 (end of BELKYRA® treatment, prior to VOLUMA™ treatment), and end of study (Exit/Visit 6; end of VOLUMA™ treatment), will be referenced in most of statistical analyses for this study.

Baseline is defined as the latest assessment prior to any study treatments for each subject. End of study is the last clinical visit an enrolled subject has in this study. For subjects who complete this study, the end of study visit will be their Visit 6 visit; for subjects who drop out

Clinical Study Protocol: CMO-MA-FAS-0513

early, they will be asked to come back for the last clinical visit for end of study data collection.

10.1.1 Analysis Populations

The following analysis populations will be used:

- Full Analysis Set (FAS) – Consists of all subjects who received BELKYRA®
- Evaluable Set (ES) – Consists of subjects in the Full Analysis Set who received BELKYRA® and VOLUMA™ and a post-treatment efficacy assessment at Visit 6 (Exit Visit).
- Safety Analysis Set (SAS) – Consists of all subjects who consented to participation. Includes subjects who are defined as Full Analysis Set as well as subjects who were biopsied but did not receive BELKYRA®

The FAS population will be used for summary of subject disposition, demographics, baseline characteristics and efficacy analyses of endpoints assessed up to end of BELKYRA® treatment; the ES population will be used for the efficacy analyses of endpoints assessed at the final study visit, and the SAS population will be used for safety analyses.

10.1.2 Subgroups

As males and females may have differing expectations / perceptions of aesthetic improvement, data will be analyzed by gender separately.

Additional subgroup analysis will be discussed in the study SAP.

10.2 DEMOGRAPHICS AND BASELINE CHARACTERISTICS

Subject disposition, demographics and baseline characteristics will be summarized using descriptive statistics.

10.3 EXPOSURE AND CONCOMITANT THERAPIES

Subject study treatment exposure and compliance will be summarized using descriptive statistics.

The latest version of the World Health Organization Drug Dictionary will be used to classify prior and concomitant medications and therapies by therapeutic class and drug/device name. Prior medication/therapy is defined as those started by enrolled subjects before the date of first study treatment. Concomitant medication/therapy is defined as those taken on or after the date of first treatment. Prior and concomitant medications/therapies will be summarized using descriptive statistics.

Clinical Study Protocol: CMO-MA-FAS-0513

10.5 EFFICACY ANALYSES

Unless stated otherwise, all efficacy analyses will compare post-treatment assessment values to the subject's corresponding baseline assessment value.

10.5.1 Primary Efficacy Analysis

Responder rate for jawline severity, which is defined as the proportion of subjects who show ≥ 1 -point improvement from baseline on the ALJDS compared to baseline assessment at the final study visit (after last VOLUMA™ treatment received) will be summarized by the number and percentage of subjects and exact 95% confidence interval will be provided.

